Screening/Data Collection Description: The anticipated process for the screening and data collection is as follows and expected to take 45 minutes. After obtaining consent via the digital informed consent tool on the iPad, the RA will assist the older adult with putting on the headphones; orient them to the iPad screen, and explain the process that will follow. First, participants will complete a demographic pre-survey. Next, they will begin VOICES with an interactive educational session about EM and APS response, and will be screened for EM. For participants who screen positive, VOICES will ask them if they would like to self-disclose. If they choose to disclose VOICES will stop and thank them for participating. If they choose not to disclose EM, they will then complete the BNI and be asked again if they would like to self-disclose.

VOICES is not intended to replace the existing protocols for handling EM in EDs. Rather it is intended to help screen and identify cases of suspected EM that otherwise will be missed. The established protocol at YNHHS when EM is suspected requires notifying the ED social worker who will conduct an in-person evaluation and decide on the best approach to handle the case. VOICES will first screen for EM and administer an interactive educational session. It will then ask if the older adult would like to self-Identify with EM. If the patient does not want to self-identify, VOICES will administer BNI and ask again if the older adult want to self-identify with EM. If the patient chooses to identify with EM, the research assistant (RA) will notify the provider/social worker and say, "The patient wants to disclose EM". When the older adult is finished they will signal to the RA who will collect the iPad, complete a brief post-survey, administer the \$20.00 incentive and (if needed) will notify their provider.

[figure not shown]

Figure 3: High Level Flow Chart of VOICES

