In this exploratory aim, we will evaluate the *positive predictive value* of VOICES as a screening tool in correctly identifying EM cases. This could serve as preliminary test for the accuracy of VOICES in correctly classifying victims/non-victims. It will be estimated through the measure of positive predictive value (PPV) using the APS case outcomes as the gold standard comparison.

Design and rational:

In Connecticut, reported cases of EM are investigated by the Protective Services for the Elderly (PSE), commonly known as APS, which is administered by the Division of Social Work Services within the Connecticut Department of Social Services (please see letter of support). PSE is designed to safeguard people age 60 and older from EM. Pursuant to State Code 2012-R-0437, mandatory reporters are able to know outcomes of their report (see letter of support from PSE). If a case was opened by PSE this means the case met the state's determined threshold for a situation requiring an investigation so reporting was valid. Often times, if a case was opened regardless of EM determination services are provided to the older adult. For our purposes, PPV is a measure of VOICES ability to correctly classify cases of clinically significant EM (true positive rate). Determination by PSE will serve as our gold-standard criterion for comparison. Ideally, VOICES would only refer cases which would require an investigation and have a positive finding of EM as this would represent true validity in identifying positive cases.

VOICES-C Study: (01/10/2020 to 03/01/2020) completed

We will conduct this activity to formally evaluate the usability of the VOICES tool. Usability refers to how easily a specific task can be accomplished with a specific tool. The International Organization for Standardization (ISO) defined usability as the "extent to which a product can be used by specified users to achieve specified goals with effectiveness, efficiency and satisfaction in a specified context of use" (ISO, 1998). Hypothesis 1a: users will report a high level of ease of use of VOICES. Hypothesis 1b: Users will report a high level of satisfaction in using VOICES.

What will subjects be asked to do?

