Risks will be minimized through appropriate participant exclusions and close medical supervision throughout the protocol. We will inform all participants that there is a chance that they may experience AE or SAE by participating in the study and that their participation is voluntary. We will also remind participants that they can discontinue participation at any time. In the Yale ED and when a member of the health care team has any suspicion of EM, he or she will notify the ED social worker who has a well-established multi-disciplinary and comprehensive protocol on how to handle the EM cases. The protocol includes any combination of the following: interview, screening (if EM is suspected but not yet identified), referral to community service provider, safety admission to the hospital, or reporting to CT Protective Services for the Elderly (PSE). The hospital, the community, PSE, and the law enforcement agencies have systems in place to maintain the abuse victim's safety.

In Summary: VOICES' goal is to help identify cases of EM within the ED visit. The subsequent procedures for the EM identification are important but are similar to the case when a provider identify suspicion of EM during normal clinical care:

- the ED already (before conducting the VOICES study) has a comprehensive and protocolized multi-disciplinary approach to respond when elder mistreatment is suspected by ED providers during usual clinical care.
- all patients who screen positive with the VOICES tool will receive a similar response.

- while the research team recognizes that the EM identified through the VOICES tool may lead to adverse events for patients associated with EM identification, we anticipate that the Yale ED's response will minimize the possible adverse events due to the EM identification.

We will train all RAs to detect common signs of distress and anxiety. If any are even suspected of being observed, our Co-I ([name]), who is a licensed clinical psychologist, will be contacted immediately for consultation and next steps, which could include counseling, referrals or a psychiatric evaluation

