Moreover, a licensed clinical psychologist will be available for consultation to the staff and patient, if needed, during most hours of recruitment. When this level of back-up is not available, we will have psychiatry back-up for any distressed reactions that require mental status evaluation. Thus, some psychological or psychiatric evaluation will be available during all study assessments and during all recruitment periods of the project to facilitate stabilization and necessary referrals for participants who report distress during assessment procedures.

If the older adult screens positive on the VOICES for EM or the older adult wants to self-disclose EM, the RA will notify the care team in the ED that there is suspicion of EM. Also, if the tool fails to identify EM but the patient would like to disclose EM, the RA will notify the care team. The RA will stay with the participant until a member of the care team arrives and implements existing protocols for handling EM in the ED.

The care team can address each patient's concerns around reporting, immediate safety concerns, and any concerns for retaliation or abandonment. The care team will contact the social worker by calling Mobile Heart Beat or his/her cell phone. The social worker will perform the Social Worker Assessment. If the assessment indicates suspicion of abuse, then the social worker will work with members of the multi-disciplinary team to handle the mistreatment case. If the case gets reported to PSE, usually PSE will arrive at the hospital within 12 hours to take care of the case. While waiting for PSE, the health care team members will discuss safety issues with the patient. If the older adult feels s/he is in immediate danger or does not feel safe going home, the care team will create a safe disposition plan that can include safety admission to the hospital until PSE can implement a more permanent solution.

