If we also exclude subjects with clear signs of EM (1 in 24) 5%, as they will be immediately identified and reported by health care provider, then we are left with EM prevalence estimation of 5.7% - 9.12%. A sample size of eight hundred subjects (N=800) should thus result in 45-72 adults from whom we can estimate the proportions who change their self-identification response and who are ready to self-disclose after using VOICES. This will be a sufficient size to estimate a 95% confidence interval around a proportion with a width of no greater than 0.3. A sample size of 800 will provide a precision of +/- 0.14 standard deviations for the 95% confidence interval around a mean for continuous feasibility outcomes (e.g. acceptability, time to completion). This sample size will also produce precision of no worse than +/- 14% in the estimation of a 95% confidence interval around a proportion for dichotomous feasibility outcomes (e.g. demand, implementation).

SECTION II: RESEARCH INVOLVING DRUGS, BIOLOGICS, RADIOTRACERS, PLACEBOS AND DEVICES

If this section (or one of its parts, A or B) is not applicable, check off N/A and delete the rest of the section.

A. RADIOTRACERS **N/A**

B. DRUGS/BIOLOGICS **N/A**

B. DEVICES **N/A**

SECTION III: RECRUITMENT/CONSENT AND ASSENT PROCEDURES

1. Targeted Enrollment: Give the number of subjects:

- Targeted for enrollment at Yale for this protocol: 800
- If this is a multi-site study, give the total number of subjects targeted across all sites:

2. Indicate recruitment methods below. Attach copies of any recruitment materials that will be used.

VOICES Feasibility Study:

 Flyers	 Internet/web postings	 Radio
 Posters	 Mass email solicitation	 Telephone
 Letter	 Departmental/Center website	 Television
 Medical record review*	 Departmental/Center research boards	 Newspaper
 Departmental/Center newsletters	 Web-based clinical trial registries	 Clinicaltrials.gov
 YCCI Recruitment database	 Social Media (Twitter/Facebook):	

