6. SAMPLE SIZE

6.1 Sample Size Determination for the Primary Outcome

Given that VOICES is a new tool, we did not have the needed information to estimate a power analysis or judge an approach sample size to calculate a meaningful sensitivity analysis when planning for the study. However, based on the initial analysis of the relevant population and our sample size, we estimate VOICES will detect EM in 40 to 70 older adults. We will report the 95% confidence intervals with our finding of sensitivity.

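### SAP 6.1 promises a confidence interval for sensitivity, which the design cannot estimate because VOICES-negatives are not systematically verified; the accuracy measure planned elsewhere is a PPV or PPV-type percentage

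*SAP*

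**What the plan says.** SAP 6.1 gives an expected 40 to 70 older adults in whom VOICES will detect elder mistreatment (EM), and then states "We will report the 95% confidence intervals with our finding of sensitivity". Sensitivity is not an outcome in SAP Table 1, section 4.2 or section 7.2.

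The other descriptions of accuracy differ from this and from one another:

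- Protocol Specific Aim 3 plans a PPV: "It will be estimated through the measure of positive predictive value (PPV) using the APS case outcomes as the gold standard comparison". The same section adds that "PPV is a measure of VOICES ability to correctly classify cases of clinically significant EM (true positive rate", and that last term is the usual name for sensitivity.
- SAP Table 1 takes the cases classified as EM as its denominator and counts those found positive by the social worker and those referred to APS. That is a PPV-type percentage, although the table does not use the term.
- SAP 4.2 and 7.2 promise only a percentage correctly classified, with no denominator and no confidence interval.

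Protocol section 11 describes who reaches a reference assessment. If the participant "screens positive on the VOICES for EM or the older adult wants to self-disclose EM, the RA will notify the care team". Independently of VOICES, "when a member of the health care team has any suspicion of EM, he or she will notify the ED social worker". A participant whom the tool misses but who wishes to disclose is also passed on.

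**The concern.** Sensitivity is true positives divided by true positives plus false negatives. The plan collects the first term, at least in part, and has no systematic means of collecting the second. A VOICES-negative participant with EM is counted only if that person volunteers a disclosure or the care team becomes suspicious. Patients with clear signs of EM are excluded beforehand, so care-team suspicion is unlikely to recover many.

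A sensitivity printed with a 95% CI would be read as a property of the screening tool. The interval would express sampling error only and would say nothing about the unverified negatives. The protocol intends a later effectiveness study, and such a figure could be carried forward into it.

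**Working it through.** **Inputs.** Planned N = 800 and prevalence in the eligible sample from protocol section 13, where "then we are left with EM prevalence estimation of 5.7% - 9.12" (per cent). Enrolled N = 1,002 from the SAP study summary. Expected detections of 40 to 70 from SAP 6.1.

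**1. The plan's own counts.** Expected cases = N × prevalence.

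- N = 800: 800 × 0.057 = 45.6 and 800 × 0.0912 = 73.0. The protocol's 45 to 72 is reproduced within rounding.
- N = 1,002: 1,002 × 0.057 = 57.1 and 1,002 × 0.0912 = 91.4. The SAP's 40 to 70 is not reproduced. It lies closer to the N = 800 counts, and the SAP gives no derivation for it.

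**2. Direction of the bias.** Let a be the share of true cases verified among VOICES-positives and b the share among VOICES-negatives. Computed sensitivity is a·TP / (a·TP + b·FN). This exceeds TP / (TP + FN) whenever b < a and FN > 0. The referral rules make b < a the likely situation, and neither b nor FN is observed.

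**3. The limiting case b = 0.** Computed sensitivity is 100% whatever FN is. Exact (Clopper-Pearson) 95% intervals:

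- 40/40: 91.2% to 100%
- 70/70: 94.9% to 100%

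**4. What the truth could be.** Assume that the detections are the VOICES-positives and all are true cases.

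| Detected | Cases | Basis for cases | Sensitivity |
|---|---|---|---|
| 40 | 91 | N = 1,002, 9.12% | 44% |
| 40 | 57 | N = 1,002, 5.7% | 70% |
| 70 | 91 | N = 1,002, 9.12% | 77% |
| 40 | 45.6 | N = 800, 5.7% | 88% |
| 70 | 73.0 | N = 800, 9.12% | 96% |

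Seventy true detections among 57 cases is impossible, so that pairing is omitted.

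**5. The same point without the prevalence figures.** Take N = 1,002 and 40 true detections, which leaves 962 negatives. Assumed EM rates of 1%, 3% and 5% among them give FN = 9.6, 28.9 and 48.1, and sensitivities of 40/49.6 = 81%, 40/68.9 = 58% and 40/88.1 = 45%. Nothing in the planned data distinguishes these.

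**6. What PPV can and cannot give.** If every positive is verified and PPV is 80% (both assumed), the exact 95% CI is 64% to 91% at 32/40 and 69% to 89% at 56/70. Verification of every positive is not assured. Under section 11 an APS outcome exists only when the case is reported. In an assumed example with 40 positives, 30 assessed and 24 confirmed, PPV is 24/30 = 80% among those assessed. It is 24/40 = 60% if the ten unassessed are counted as not confirmed. The choice of denominator therefore matters and has to be written down.

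**The case against.** The strongest reply is that sensitivity is a slip of the pen. It appears in the sample-size section, not in the outcomes or the analytic plan. The same paragraph uses the phrase sensitivity analysis loosely, and the protocol's gloss on PPV invites the confusion. This is plausible, and a reader should not infer from SAP 6.1 that a sensitivity calculation is a settled part of the analysis. But the sentence directly follows the expected number of detections, so diagnostic sensitivity is its natural reading. If PPV was meant, the sentence still names the wrong statistic.

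A reader might also infer that true sensitivity is 44% to 70% and that any computed interval would lie wholly above it. The documents do not support that. The range divides 40, an underived SAP figure, by cases at N = 1,002. Against the N = 800 counts, which 40 to 70 resembles, sensitivity is 88% to 96%. With 70 detections at N = 1,002, sensitivity would be 77% or higher. The computed intervals of 94.9% to 100% (70/70) and 85.1% to 97.8% (70/75, if five missed cases happened to surface) fall inside 77% to 100%. The error may be large or small.

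It is also fair to say that PPV suffers from incomplete verification. That stands. Section 11 says "all patients who screen positive with the VOICES tool will receive a similar response", whereas the protocol's Screening/Data Collection Description says "If the patient chooses to identify with EM, the research assistant (RA) will notify the provider/social worker". Reconciling those two passages is a separate matter. It bears on this point only because it leaves open how many positives will have a reference result.

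**Conclusion.** The point holds. The plan provides no systematic reference assessment of VOICES-negative, non-disclosing participants, so sensitivity is not estimable. Any computed value would tend to be too high, by an amount the data cannot reveal. This follows from the referral rules and needs no numerical assumption.

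The size is open. The illustrations run from about 44% (40 detected, 91 cases at N = 1,002) to about 88% to 96% (40 to 70 detected, 45.6 to 73.0 cases at N = 800), all assuming that every detection is a true case. None of them estimates the tool's performance.

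Whether the sentence is meant literally or loosely, it disagrees with protocol Aim 3 and SAP Table 1. SAP 4.2 and 7.2 add a further undefined description. The consequence is limited: accuracy is an exploratory outcome, and participation and usage are untouched.

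**What to change.** - **SAP 6.1:** replace the sentence with a statement that PPV will be reported with an exact 95% CI.
- **SAP 4.2 and 7.2:** use the same measure in place of the percentage correctly classified.
- **Definition of positive:** state which VOICES result counts for accuracy. The protocol names the EASI-sa as the screener, while the SAP measures demand by self-identification and does not say which applies here.
- **Denominator:** VOICES-positives with a completed reference assessment, separately for the social worker assessment and the APS outcome (in Connecticut, Protective Services for the Elderly). Report the number of positives not assessed or not referred, and give as a bound the result with these counted as not confirmed.
- **Protocol Aim 3:** delete the parenthesis that equates PPV with the true positive rate.
- **Limitation:** state that sensitivity, specificity and negative predictive value are not estimable because negatives are not systematically verified.

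The cost is wording only, with no new data. The price is a narrower claim: nothing can be said about missed cases, and a PPV against APS applies only to the positives who were referred.

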7 ANALYTIC PLAN

7.1 Analysis of Primary Outcome:

Implementation in Terms of Participation. Participation will be determined by the ratio of participants who are successfully enrolled to the total number of eligible patients. The numerator, denominator, frequencies and 95% confidence intervals will be reported.

Implementation in Terms of Usage. Usage will be determined by the number of consented participants enrolled in the study who used VOICES to completion. The numerator, denominator, frequencies and 95% confidence intervals will be reported.

7.2 Analysis of Other Pre-Specified Outcomes

Acceptability: Participant satisfaction will be measured along multiple dimensions using post-use satisfaction survey with two 5-point Likert response set scales, developed by the research team. Scale 1: Likert scale 1-5, where 1= Very Dissatisfied, and 5= Very Satisfied Scale 2: Likert scale 1-5, where 1= Strongly Disagree, and 5= Strongly Agree. The means and standard deviations will be reported.

Demand: Demand will be assessed through examining how likely will VOICES be used by patients. To do this, the size of target population of EM victims in the ED will be measured by the % of the patients who self-identified with elder mistreatment and the % who receive the Brief Negotiation Interview (BNI) portion of VOICES. Counts of participants will be reported.

Practicality: Practicality will be assessed by observing the ease of VOICES use by patients. To do this, a series of steps will be watched to determine the efficiency of implementation measured by the average time (1) to consent & orient participants to the tool and (2) needed to complete VOICES documented by the Research Assistant; and (3) patients perceived time of VOICES as measured on post-survey. Each of these will be reported as part of the overall outcome. The means and standard deviations will be reported.

Efficacy of the Educational Material: To understand the efficacy of VOICES in this pilot, we will look at how many participants changed their self-identification response after completing the educational component. Counts of participants will be reported.

Efficacy of the Brief Negotiation Interview: We will look at how many patients changed their readiness to identify and readiness to disclose after completing the Brief Negotiation Interview (BNI). Counts of participants will be reported.

Efficacy of Self-Identification on Self-Disclosure: We will explore whether self-identification impacts likelihood of self-disclosure. Counts of participants who change willingness to disclose among those that self-identify will be reported.

Accuracy: To understand the accuracy of the VOICES tool, a preliminary evaluation of the accuracy of VOICES as a screening tool in correctly classifying EM cases that were positive based on social worker assessment, and those referred to Adult Protective Services (APS). The percent correct classification will be reported.
